5.5 Derived Variables

All questionnaire scores will be derived by Biostatistics in the ADaM datasets using the formulas defined below, even if calculated scores are present in the EDC database. All pre-calculated scores will be ignored for analysis.

- With the following exception, vIGA-AD Success = vIGA-AD of ‘Clear’ (0) or ‘Almost Clear’ (1) plus at least a 2-grade improvement from Baseline. The exception is that for subjects who discontinued early from study due to an AE or lack of efficacy, the subject will be considered as not having a vIGA-AD success (for MI and non-responder imputation analyses) or missing (for observed case analyses) for all pre-specified analysis visits (refer to Section 5.4) for which the subject’s last dose day falls within analysis visit window or is prior to the start of the analysis visit window.
- Average weekly WI-NRS = Average weekly WI-NRS pruritus score will be calculated as the sum of the daily WI-NRS scores reported during a specific week (in a 7-day period; refer to Section 5.4) of the study divided by the number of days with non-missing scores for that week. A minimum of 4 days of observations are needed to calculate an average weekly WI-NRS pruritus score. Otherwise, the corresponding average weekly WI-NRS pruritus score will be considered missing.
- With the following exception, a WI-NRS success = achievement of a 4- point reduction in average weekly WI-NRS pruritus score compared to average weekly WI-NRS baseline, calculated only for the subjects with average weekly WI-NRS score of ≥ 4 at baseline. The exception is that for subjects who discontinued early from study due to an AE or lack of efficacy, the subject will be considered as not having a WI-NRS success (for MI and non-responder imputation analyses) or missing (for observed case analyses) for all pre-specified analysis visits (refer to Section 5.4) for which the subject’s last dose day falls within the analysis visit window or is prior to the start of the analysis visit window.
- EASI total score = $0.2 (E_h + I_h + Ex_h + L_h) A_h + 0.2 (E_u + I_u + Ex_u + L_u) A_u + 0.3 (E_t + I_t + Ex_t + L_t) A_t + 0.3 (E_l + I_l + Ex_l + L_l) A_l$

where E, I, Ex, L, and A denote erythema, induration, excoriation, lichenification, and area, respectively, and h, u, t, and l denote head, upper extremities, trunk, and lower extremities, respectively. Scalp, palms, and soles may be treated with investigational product in this study but will be excluded from the EASI assessment.

- With the following exception, EASI-50, EASI-75, EASI-90, and EASI-100 = Achievement of at least a 50%, 75%, 90%, or 100% reduction from baseline in EASI total score,

 Innovaderm Research ■■■	STATISTICAL ANALYSIS PLAN, Version 1.0
Protocol Number: ARQ-151-315	Sponsor: Arcutis Biotherapeutics, Inc.

respectively. The exception is that for subjects who discontinued early from study due to an AE or lack of efficacy, the subject will be considered as not having reached EASI-50, EASI-75, EASI-90 and EASI-100 (for MI and non-responder imputation analyses) or missing (for observed case analyses) for all pre-specified analysis visits (refer to Section 5.4) for which the subject's last dose day falls within the analysis visit window or is prior to the start of the analysis visit window.

- CDLQI Score = sum of the 10 questions (individual questions scored as Very much=3, Quite a lot=2, Only a little=1, Not at all=0; Question 7: if the last week was school time, the question was scored as Very much=3, Quite a lot=2, Only a little=1, Not at all=0, with Prevented school recoded to 3, and if the last week was holiday time, the standard responses apply), ranging from 0 to 30. If 1 item is missing, that item is scored as 0. If 2 or more items are missing, the score should not be calculated.
- IDQoL Score = sum of the 10 questions (ranging from 0 to 3), resulting in a score ranging from 0 to 30. The higher the score, the more quality of life is impaired. If 1 item is missing, that item is scored as 0. If 2 or more items are missing, the score should not be calculated. The severity of dermatitis is scored separately, and it is not included in the IDQoL total score.
- DFI Score = sum of the 10 questions (individual questions scored as Very much=3, A lot=2, A little=1; Not at all=0), ranging from 0 to 30. If 1 item is missing, it is scored as 0 for that item. If 2 or more items are missing, the score should not be calculated.
- POEM = sum of the 7 questions (individual questions scored as No days = 0, 1 to 2 days = 1, 3 to 4 days = 2, 5 to 6 days = 3, Every day = 4), ranging from 0 to 28. If 1 question is left unanswered this is scored 0 and the scores are summarized and expressed as usual out of a maximum of 28. If 2 or more questions are left unanswered the questionnaire is not scored.
- SCORAD = [Overall BSA affected by AD / 5] + [Intensity score*7/2] + subjective symptoms score (pruritus + sleep loss); SCORAD score will be set to missing if information for any of the three measures is missing.

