8.2. Efficacy Evaluation

8.2.1. Statistical Methods

Subjects will be stratified by Baseline vIGA-AD score and by study site, however due to a very low number of subjects in many sites, the analysis model will only stratify by vIGA-AD score stratum.

The primary endpoint will be tested using ITT population.

The primary estimand is described by the following attributes:

Treatment: Roflumilast cream 0.05%

Population: Subjects aged 2-5 years with Atopic Dermatitis

Endpoint: vIGA-AD success at Week 4

Handling of Intercurrent Events: A hybrid strategy will be used for handling intercurrent events. For events other than discontinuation due to AE or lack of efficacy (LoE), the occurrence of the intercurrent event will be considered irrelevant in defining the treatment effect of interest, i.e., the value for the variable of interest is used regardless of whether the intercurrent event occurs. This is the treatment policy strategy. Discontinuation due to an AE or LoE is considered to be informative about the subject's outcome and is incorporated into the definition of the variable. To that end, subjects who discontinue due to LoE or AE will be treated as non-responders for an analysis visit if the study day of the subject's last dose day falls within or prior to the relevant analysis visit window. Analysis visit windows will be defined in the SAP. This is a composite variable strategy.

Population-level Summary: The ratio of the odds of achieving vIGA-AD success after 4 weeks of using roflumilast cream 0.05%, relative to the odds of success after 4 weeks using a matching vehicle cream in the ITT population.

Missing data will be handled with multiple imputation methods (MI). A Cochran-Mantel-Haenszel (CMH) test stratified by the baseline vIGA-AD score used for randomization, will be performed separately for each of the multiply imputed analysis data sets, and results will be combined into one multiple imputation inference. The CMH test will not be stratified by study site as the 650 subjects will be randomized by over 90 sites leading to a low subject to site ratio. The common Mantel-Haenszel (MH) odds ratio and common MH proportion difference, adjusted for baseline vIGA-AD score used for randomization, will be provided along with their associated 97.5% and 95% CIs. Statistical significance will be concluded at the 2.5% significance level (2-sided).

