To control for the familywise type I error at level of 0.025, the remaining secondary endpoints will be tested sequentially at an alpha level of 0.025 upon successful demonstration of statistical significance for the primary endpoint. The endpoints listed below will be tested in ITT population unless otherwise noted.

- In subjects with a vIGA-AD score of 'Moderate' at randomization, IGA Success at Week 4
- Achievement of at least 75% reduction in the Eczema Area and Severity Index (EASI-75) at Week 4
- vIGA-AD score of 'clear' or 'almost clear' at Week 4
- vIGA-AD Success at Week 2
- vIGA-AD of 'clear' or 'almost clear' at Week 2
- vIGA-AD success at Week 1
- vIGA-AD of 'clear' or 'almost clear' at Week 1

The ITT population will be used for the primary and secondary efficacy analyses endpoints except the endpoint for subjects with vIGA-AD score of 'Moderate' at baseline, in which vIGA-AD Moderate ITT population will be used.

A supplemental analysis of observed data for the PP population will also be performed for the primary endpoint, vIGA-AD success at Week 4. Descriptive statistics for continuous variables will include mean, median, standard deviation, Q1, Q3, min, max. Descriptive statistics for categorical variables will include frequencies and percentages. For missing data, the primary imputation method and sensitivity methods will be detailed in the SAP. The secondary endpoint of vIGA-AD success in subjects with vIGA-AD of 'Moderate' at randomization will be analyzed with a chi-square test.

Other categorical efficacy endpoints will be analyzed in the same manner as the primary endpoint.

8.2.2. Children's Dermatology Life Quality Index (CDLQI), Infant Dermatology Quality of Life Index (IDQoL), SCORAD and POEM

Children's Dermatology Life Quality Index (CDLQI), the Infant Dermatology Quality of Life Index (IDQoL), the Dermatitis Family Impact (DFI), the Scoring Atopic Dermatitis (SCORAD), and the Patient Oriented Eczema Measure (POEM) will be analyzed by evaluation of the reduction in total score at Week 4. These efficacy endpoints will be analyzed descriptively.

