12 EFFICACY ANALYSIS

12.1 Primary Efficacy Endpoint Analysis

12.1.1 Primary Efficacy Endpoint and Estimand

The vIGA-AD is a static evaluation of qualitative overall AD severity. This global assessment scale is an ordinal scale with five severity grades (reported only in integers of 0 to 4). Each grade is defined by a distinct and clinically relevant morphologic description that minimizes inter-observer variability. vIGA-AD is evaluated for the entire body except the scalp, palms, and soles.

The primary efficacy endpoint is vIGA-AD success, defined as an vIGA-AD score of ‘clear’ (0) or ‘almost clear’ (1) plus at least a 2-grade improvement from Baseline at Week 4.

The primary estimand is described by the following attributes:

Population: Patients with Atopic Dermatitis

Endpoint: vIGA-AD success at Week 4

Intercurrent events: In the course of the 4-week randomized treatment period, subjects may be exposed to possible known or unknown intercurrent events that could possibly impact the estimates of the estimand, such as treatment discontinuation due to a specific adverse effect or perhaps a lack of effect. A composite strategy will be implemented that handles subjects who discontinue due to lack of efficacy or adverse event as missing not at random differently than all other subjects. That is, subjects who discontinue due to lack of efficacy or adverse event will be treated as non-responders for all pre-specified analysis visits (refer to Section 5.4) for which the subject’s last dose day falls within the analysis window or is prior to the start of the analysis window (refer to Section 5.5) while the “Treatment Policy Strategy” will be adopted for handling intercurrent events in this study other than discontinuation due to lack of efficacy or adverse event.

Population-level summary: ratio of the odds of achieving vIGA-AD success after 4 weeks of using roflumilast cream 0.05%, relative to the odds of success after 4 weeks using a matching vehicle cream in the ITT population.

The supportive population-level summary: the proportion difference between Roflumilast cream 0.05% and vehicle groups will be provided for the patients who achieve vIGA-AD success at week 4 in the ITT population.

 Innovaderm Research ■■■	STATISTICAL ANALYSIS PLAN, Version 1.0
Protocol Number: ARQ-151-315	Sponsor: Arcutis Biotherapeutics, Inc.

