12.1.3 Primary Endpoint Analysis

For the primary analysis, missing vIGA-AD scores will be imputed using multiple imputation as described in Section 6.2.1. These imputations will result in a minimum of 25 to a maximum of 250 complete analysis datasets, depending on the number of imputed monotone datasets that are required.

Percentages of subjects having a vIGA-AD Success (refer to Section 12.1.1) will be presented by visit and treatment group based on multiply imputed data in the ITT population along with both 97.5% and 95% Wilson CIs. The common MH odds ratio and common MH proportion difference, adjusted for the randomization factor (i.e., randomized vIGA-AD score) will also be provided along with their common associated 97.5% and 95% CIs. Additionally, count and percentage of subjects having a vIGA-AD success, count and percentage of subjects in each category of the vIGA-AD scale, and descriptive statistics for the vIGA-AD scores, change in vIGA-AD score from baseline and percent change in vIGA-AD score from baseline will be presented by visit and treatment group based on observed data in the ITT population.

The primary endpoint (vIGA-AD Success at Week 4) will then be analyzed using multiple imputation CMH test stratified by randomized baseline vIGA-AD. To do so, a CMH analysis will be performed separately for each of the complete multiply imputed analysis data sets, and results will be combined into one multiple imputation inference using the methodology described in Section 6.2.1. Statistical significance will be concluded at the 2.5% significance level (2-sided). Should the odds ratio be not estimable for at least one multiply imputed dataset, the conclusion of

 Innovaderm Research ■■■	STATISTICAL ANALYSIS PLAN, Version 1.0
Protocol Number: ARQ-151-315	Sponsor: Arcutis Biotherapeutics, Inc.

the study will be based on the p-value obtained from a MH test, stratified by randomized baseline vIGA-AD, for the common MH proportion difference at Week 4.

The following sensitivity and supplemental analyses to the primary analysis of the primary endpoint will be performed:

- Tipping Point analysis (refer to Section [6.2.3](#)) on ITT population.
- Non-responder imputation (refer to Section [6.2.2](#)) on ITT population.
- Observed data on ITT population (refer to Section [4.1](#)).
- Observed data on PP population (refer to Section [4.2](#)).

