100%, where a subject's palm represents 1% of his/her total BSA). Secondly, the AD severity is evaluated based on 6 items (erythema, edema/papulation, oozing/crusts, excoriation, lichenification, and dryness) graded using a 4-point scale (half steps are not allowed): 0 (absence), 1 (mild), 2 (moderate), and 3 (severe). Lastly, 2 subjective items (loss of sleep and intensity of pruritus) are evaluated by having the subject indicates on a 10.0 cm visual analog scale (VAS) the point corresponding to the average value over the last 3 days (0 cm = none to 10 cm= maximum).

- The POEM is a tool used for monitoring atopic eczema severity. It focus on the illness as experience by the subject. It consists of a 5-point scale measuring the frequency of each of 7 AD symptoms (i.e., dryness, itching, flaking, cracking, sleep loss, bleeding, and weeping) over the past week scored from 0 (no days), 1 (1 to 2 days), 2 (3 to 4 days), 3 (5 to 6 days), and 4 (every day).

For subjects who discontinue due to lack of efficacy or adverse event, efficacy data assigned to a pre-specified analysis visit will be removed from observed data if subject's last dose day falls within the analysis visit window or is prior to the start of the analysis visit window used to assign data to a pre-specified analysis visit. This will be true for all endpoints described above.

For the continuous exploratory efficacy endpoints of change and percent change from baseline in average weekly WI-NRS, EASI total score, % BSA, CDLQI/IDQoL score (+ severity of dermatitis), DFI score, SCORAD score, and POEM score at Week 1, Week 2, Week 3 (WI-NRS only), and Week 4, descriptive statistics for the score, change from baseline and percent change from baseline will be presented by visit and treatment group based on observed data in the ITT population. For the continuous other efficacy endpoint of daily WI-NRS, descriptive statistics will also be presented similarly on a daily basis. Additionally, a plot of the mean (and standard error) daily WI-NRS scores over time for each treatment group will also be provided based on observed data. A similar plot will be provided for the percent change from baseline in daily WI-NRS.

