12.5 Summary of Primary and Secondary Efficacy Analysis

Table 5 provides a summary of the primary and sensitivity analyses that will be provided for primary and secondary efficacy endpoints.

Table 5 Summary of Primary and Secondary Efficacy Analyses

Efficacy Endpoint	Primary Analysis	Sensitivity Analysis
Primary (refer to Section 12.1)		
vIGA-AD Success (a score of '0' or '1' plus at least a 2-grade improvement) at week 4	ITT, multiple imputation (CMH)	#1 ITT, Tipping point (CMH)) #2 ITT, non-responder imputation (CMH) #3 ITT, observed data (CMH) #4 PP, observed data (CMH)
Secondary (refer to Section 12.2)		
vIGA-AD Success (a score of '0' or '1' plus at least a 2-grade improvement) at week 4	vIGA-AD Moderate ITT, multiple imputation (chi- square)	#1 vIGA-AD Moderate ITT, non- responder imputation (chi-square) #2 vIGA-AD Moderate ITT, observed data (chi-square)
-EASI-75 at week 4 -vIGA-AD score of '0' or '1' at week 4 -vIGA-AD Success at week 2 -vIGA-AD score of '0' or '1' at week 2 -vIGA-AD Success at week 1 -vIGA-AD score of '0' or '1' at week 1	ITT, multiple imputation (CMH)	#1 ITT, non-responder imputation (CMH) #2 ITT, observed data (CMH)

 Innovaderm Research	STATISTICAL ANALYSIS PLAN, Version 1.0
Protocol Number: ARQ-151-315	Sponsor: Arcutis Biotherapeutics, Inc.

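### The observed-data analyses set children who stop for an adverse event or lack of efficacy to missing, although the estimand counts them as non-responders, so analyses listed as sensitivity analyses target a different quantity

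*SAP*

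**What the plan says.** **Estimand.** Protocol 8.2.1 uses a composite strategy for stopping because of AE or LoE: "subjects who discontinue due to LoE or AE will be treated as non-responders for an analysis visit" when the last dose day lies within or before that visit's window. SAP 12.1.1 agrees: "subjects who discontinue due to lack of efficacy or adverse event will be treated as non-responders for all pre-specified analysis visits" meeting the same condition. All other intercurrent events follow treatment policy.

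**Derivation.** SAP 5.5 applies this rule to vIGA-AD success in the multiple-imputation and non-responder analyses, but adds "or missing (for observed case analyses"). It repeats the wording for WI-NRS success and for EASI-50, -75, -90 and -100. It gives no derivation, and so no such rule, for the three clear-or-almost-clear secondary endpoints (Weeks 4, 2 and 1).

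**Where the rule is used.** SAP 12.1.3 introduces four further analyses of the primary endpoint with "The following sensitivity and supplemental analyses to the primary analysis of the primary endpoint will be performed". One is "Observed data on ITT population" and another is the per-protocol (PP) equivalent. Table 5 (SAP 12.5) lists both in its sensitivity column: "3 ITT, observed data (CMH) #4 PP, observed data (CMH"). Protocol 8.2.1 gives the PP analysis a different label: "A supplemental analysis of observed data for the PP population will also be performed for the primary endpoint". For every secondary endpoint, SAP 12.2 names two sensitivity analyses, one of them on observed data.

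**Exploratory endpoints.** SAP 12.3 has a parallel rule for AE/LoE discontinuers: "efficacy data assigned to a pre-specified analysis visit will be removed from observed data" under the same last-dose condition.

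**The concern.** Under a composite strategy the outcome of an AE/LoE discontinuer is not missing. It is known by definition, and it is failure. Setting it to missing removes the child from the denominator because of that outcome.

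A sensitivity analysis should vary the missing-data assumptions while keeping the estimand fixed. The observed-data analyses change two things at once: they stop imputing, and they drop the composite handling of AE/LoE. If such an analysis differs from the primary result, the reader cannot tell from it alone which change is responsible.

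The analyses affected are:

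- ITT and PP observed data for the primary endpoint;
- observed data for vIGA-AD success in the Moderate ITT population, EASI-75 at Week 4, and vIGA-AD success at Weeks 2 and 1;
- observed-data summaries of the exploratory responder endpoints that SAP 5.5 covers.

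The rule can also discard a score that was collected. An early termination visit includes the Week 4 procedures (Protocol 7.5) and can supply the Week 4 value if it falls on Days 23 to 43 (SAP 5.4, Table 2). Suppose a child takes the last dose on Day 20, stops for LoE and is scored moderate on Day 24. That is an observed Week 4 failure, and the observed-data analysis deletes it.

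**Working it through.** **1. The plan's power figure.** Inputs from the sample-size sections (Protocol synopsis and 8.1.1, SAP 5.1): 433 active, 217 vehicle, 37% vs 22%, two-sided alpha 0.025. I use a pooled-variance normal approximation without strata.

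- Pooled rate = (433 × 0.37 + 217 × 0.22)/650 = 0.320.
- Null SE = √[0.320 × 0.680 × (1/433 + 1/217)] = 0.0388.
- Alternative SE = √(0.37 × 0.63/433 + 0.22 × 0.78/217) = 0.0365.
- Power = Φ[(0.15 − 2.241 × 0.0388)/0.0365] = 95.8%, in line with the stated figure of over 90%.
- The Moderate subset, with 490 assumed to split 327/163, gives 88.2%, in line with the stated figure of over 80%.

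The rule does not enter these figures.

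**2. Effect of dropping defined failures.** Let p be an arm's success rate with AE/LoE discontinuers counted as failures, and d the share of the arm dropped. Successes stay at p and the denominator falls to 1 − d.

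- Observed-data rate = p/(1 − d)
- Observed-data odds = p/(1 − p − d)

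The planning rates are taken as the composite rates, and data missing for other reasons are ignored. Every d below is an assumption, because the documents state no AE/LoE stopping rate.

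| Dropped, active / vehicle | Active | Vehicle | Difference (points) | Odds ratio |
|---|---|---|---|---|
| 0% / 0% (counted as failures) | 37.0% | 22.0% | 15.0 | 2.08 |
| 2% / 2% | 37.8% | 22.4% | 15.3 | 2.10 |
| 5% / 5% | 38.9% | 23.2% | 15.8 | 2.12 |
| 10% / 10% | 41.1% | 24.4% | 16.7 | 2.16 |
| 6% / 2% | 39.4% | 22.4% | 16.9 | 2.24 |
| 2% / 5% | 37.8% | 23.2% | 14.6 | 2.01 |
| 2% / 10% | 37.8% | 24.4% | 13.3 | 1.87 |

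Example, 6%/2%: 0.37/0.94 = 0.394 and 0.22/0.98 = 0.224; difference 16.9 points.

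**3. Direction.** An arm's rate rises by p × d/(1 − d). The difference is unchanged when d/(1 − d) on vehicle is 0.37/0.22 = 1.68 times its value on active. With 2% dropped on active, that is 3.3% on vehicle; above that the difference shrinks. The odds ratio is unchanged when d(vehicle)/0.78 = d(active)/0.63, so it shrinks once vehicle stopping exceeds 1.24 times active stopping.

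**4. Borderline results.** These are illustrative counts with a pooled z test, unstratified.

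- 128/433 vs 48/217 gives p = 0.044. Dropping 5%/2% gives 128/411 vs 48/213 and p = 0.024.
- 132/433 vs 48/217 gives p = 0.0246. Dropping 2%/5% gives 132/424 vs 48/206 and p = 0.041.

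An observed-data result can therefore cross 0.025 in either direction through this rule alone.

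**The case against.** The rule is explicit, prespecified and written the same way wherever SAP 5.5 uses it. One can argue that observed-case should mean what it says, that filling in failures makes it a partial non-responder imputation, and that full non-responder imputation is already planned for the primary and all secondary endpoints. A supplemental analysis may also target another quantity, and the protocol calls the PP analysis supplemental. This part stands: the point concerns analysis choice and labelling, and is not a contradiction. It does not settle the matter, because Table 5 and SAP 12.2 call these sensitivity analyses and nowhere state the changed target.

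Several stronger readings are tempting but not supported:

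- *All the sensitivity analyses drop failures.* They do not. Non-responder imputation (SAP 6.2.2) and the tipping point (SAP 6.2.3) keep these children as non-responders.
- *The rule favours active treatment.* Rates rise in any arm that loses children, but the rule covers LoE as well as AE, and enough extra stopping on vehicle shrinks the effect.
- *The results cannot be interpreted.* They will sit beside the other analyses. Reasons for study discontinuation are tabulated by arm (SAP 7.1), so a reader can largely gauge how many children were removed.
- *Every secondary endpoint is affected.* SAP 5.5 states no such rule for clear or almost clear.
- *The continuous analyses in SAP 12.3 are equally wrong.* The SAP sets no estimand for them that requires post-discontinuation scores, and their p-values are nominal. Keeping those scores would be a switch to treatment policy, which is debatable.

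PP is also a weak example. Entry requires a Week 4 vIGA-AD assessment in window and at least 80% compliance, which will exclude most early stoppers. Not necessarily all: SAP 11 counts expected applications only up to the last treatment or interruption date, so an early stopper can reach 80%.

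**Conclusion.** The point holds for the observed-data responder analyses. They drop children whom the estimand defines as failures, and they are presented as sensitivity analyses for an estimand they do not target.

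The size depends on AE/LoE stopping rates that the documents do not give. At 2% per arm or less, each arm's rate moves by under one point and the difference by about 0.3 points. Over the scenarios tabulated, the 15.0-point difference becomes anything from 13.3 to 16.9. These figures assume that the planning rates already count AE/LoE discontinuers as failures.

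A reader might infer that the trial's main conclusion is at risk. It is not: the primary multiple-imputation analysis, the testing sequence and the power calculation do not use this rule. The effect in PP is likely to be small. The change is still worth making before unblinding, because these results will be read as evidence of robustness.

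**What to change.** 1. In SAP 5.5, replace "or missing (for observed case analyses") for vIGA-AD success, EASI responses and WI-NRS success, so that AE/LoE discontinuers count as non-responders in the observed-data analyses too, under the existing last-dose condition. Leave missing only values that are missing for other reasons.
2. Add a derivation for clear or almost clear with the same rule, since SAP 5.5 has none.
3. Make no change to the continuous exploratory analyses in SAP 12.3. Add only a clause saying that SAP 5.5 governs responder endpoints there, so that the two sections agree.
4. If a pure observed-case analysis is kept as well, label it supplementary in SAP 12.1.3, SAP 12.2 and Table 5, state its different target, and report by arm and visit how many children the rule removed.

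The cost is SAP wording and one derivation flag, with no new data. The downside is slightly lower observed-data success rates.
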